### Subject Population:

Subjects diagnosed with gout eligible for this study will have sUA  $\geq 6$  mg/dL and inability to maintain sUA  $< 6$  mg/dL on other urate lowering therapy, or intolerable side effects associated with current urate-lowering therapy, or with a contraindication to xanthine oxidase inhibitor therapy.

### **Inclusion Criteria:**

Eligible subjects must meet/provide **all** of the following criteria:

1. Willing and able to give informed consent.
2. Willing and able to comply with the prescribed treatment protocol and evaluations for the duration of the study.
3. Adult men or women  $\geq 18$  years of age.
4. Uncontrolled gout, defined as meeting the following criteria:
  - Hyperuricemia during the screening period defined as sUA  $\geq 6$  mg/dL and;
  - Failure to maintain normalization of sUA with xanthine oxidase inhibitors at the maximum medically appropriate dose, or with intolerable side effects or a contraindication to xanthine oxidase inhibitor therapy based on medical record review or subject interview and;
  - Symptoms of gout including at least 1 of the following:
    - Presence of at least one tophus
    - Recurrent flares defined as 2 or more flares in the past 12 months prior to screening
    - Presence of chronic gouty arthritis
5. Willing to discontinue all oral urate-lowering therapy at least 7 days prior to MTX dosing at Week -4 and remain off of urate lowering therapy when receiving pegloticase infusions during the study.
6. Women of childbearing potential (including those with an onset of menopause  $<2$  years prior to screening, non-therapy-induced amenorrhea for  $<12$  months prior to screening, or not surgically sterile [absence of ovaries and/or uterus]) must have negative serum/urine pregnancy tests during Screening:
  - Subjects must agree to use 2 reliable forms of contraception during the study, one of which is recommended to be hormonal, such as an oral contraceptive. Hormonal contraception must be started  $\geq 1$  full cycle prior to Week -4 (start of MTX) and continue for 30 days after the last dose of pegloticase, or at least one ovulatory cycle after the last dose of MTX (whichever is the longest duration after the last dose of pegloticase). Highly effective contraceptive methods (with a failure rate  $<1\%$  per year), when used consistently and correctly, include implants, injectables, combined oral contraceptives, some intrauterine devices, sexual abstinence, or vasectomized partner.
7. Men who are not vasectomized must agree to use appropriate contraception so as to not impregnate a female partner of reproductive potential during the study, beginning

with the initiation of MTX at Week -4 and continuing through 3-Month Post-Treatment Follow-up.

8. Able to tolerate MTX 15 mg for 4 weeks during the MTX Run-in Period prior to the first dose of pegloticase.

**Exclusion Criteria:**

Subjects will be ineligible for study participation if they meet **any** of the following criteria:

1. Weight >160 kg (352 pounds) at Screening.
2. Any serious acute bacterial infection, unless treated and completely resolved with antibiotics at least 2 weeks prior to Week -4 Visit.
3. Severe chronic or recurrent bacterial infections, such as recurrent pneumonia or chronic bronchiectasis.
4. Current or chronic treatment with systemic immunosuppressive agents such as MTX, azathioprine, or mycophenolate mofetil; prednisone  $\geq$ 10 mg/day or equivalent dose of other corticosteroid on a chronic basis (defined as 3 months or longer) would also meet exclusion criteria.
5. Known history of any solid organ transplant surgery requiring maintenance Immunosuppressive therapy unless treated and no chronic or active infection confirmed by HBV serology.
6. Known history of hepatitis B virus surface antigen positivity or hepatitis B DNA positivity, unless treated and viral load is negative and no chronic or active infection confirmed by HBV serology.
7. Known history of hepatitis C virus RNA positivity unless treated and viral load is negative.
8. Known history of Human Immunodeficiency Virus (HIV) positivity.
9. Glucose-6-phosphate dehydrogenase (G6PD) deficiency (tested at Screening Visit).
10. Severe chronic renal impairment (estimated glomerular filtration rate  $<40$  mL/min/1.73 m^2) at the Screening Visit based on 4 variable-Modification of Diet in Renal Disease [MDRD] formula or currently on dialysis.
11. Non-compensated congestive heart failure or hospitalization for congestive heart failure or treatment for acute coronary syndrome (myocardial infarction or unstable angina) within 3 months of the Screening Visit, or current uncontrolled arrhythmia, or current uncontrolled blood pressure (BP) ( $>160/100$  mmHg) prior to Week -4.
12. Pregnant, planning to become pregnant, breastfeeding, planning to impregnate female partner, or not on an effective form of birth control, as determined by the Investigator.
13. Prior treatment with pegloticase (KRYSTEXXA), another recombinant uricase (rasburicase), or concomitant therapy with a polyethylene glycol-conjugated drug.

14. Known allergy to pegylated products or history of anaphylactic reaction to a recombinant protein or porcine product.
15. Contraindication to methotrexate (MTX) treatment or MTX treatment considered inappropriate.
16. Known intolerance to MTX.
17. Receipt of an investigational drug within 4 weeks or 5 half-lives, whichever is longer, prior to MTX administration at Week -4, or plans to take an investigational drug during the study.
18. Liver transaminase levels (AST or ALT) > upper limit of normal (ULN) or albumin < the lower limit of normal (LLN) at the Screening Visit.
19. Chronic liver disease.
20. White blood cell count < 4,000/ $\mu$ l, hematocrit < 32 percent, or platelet count <75,000/ $\mu$ l.
21. Currently receiving systemic or radiologic treatment for ongoing cancer.
22. History of malignancy within 5 years other than non-melanoma skin cancer or in situ carcinoma of cervix.
23. Uncontrolled hyperglycemia with a plasma glucose value >240 mg/dL at Screening that is not subsequently controlled by the end of the Screening.
24. Diagnosis of osteomyelitis.
25. Known history of hypoxanthine-guanine phosphoribosyl-transferase deficiency, such as Lesch-Nyhan and Kelley-Seegmiller syndrome.
26. Unsuitable candidate for the study, based on the opinion of the Investigator (e.g., cognitive impairment), such that participation might create undue risk to the subject or interfere with the subject's ability to comply with the protocol requirements or complete the study.
27. Alcohol use in excess of 3 alcoholic beverages per week.
28. A known intolerance to all protocol standard gout flare prophylaxis regimen (i.e. colchicine and/or non-steroidal anti-inflammatory drugs and/or low-dose prednisone  $\leq$ 10 mg/day).
29. Currently receiving urate-lowering therapies and unable to discontinue treatment at least 7 days prior to MTX dosing at Week -4 and remain off of urate lowering therapy when receiving pegloticase infusions during the study.
30. Current pulmonary fibrosis, bronchiectasis or interstitial pneumonitis. If deemed necessary by the Investigator, a chest X-ray may be performed during Screening.

**Dose Regimen/Route of Administration:**

**MTX:**

During the MTX Run-in Period, which begins 4 weeks prior to the first dose of pegloticase, subjects will take oral MTX at a dose of 15 mg weekly.

Subjects will be instructed to take MTX weekly on the same day each week [(if dosing more frequently than once in a day (i.e. BID, TID)], the total weekly MTX dose should be taken within 24 hours, preferably the same calendar day) and record the date and time of each dose in the dosing calendar.

During the MTX Run-in Period, if a dose is missed, it should be taken as soon as it is remembered. If it is within 48 hours of the next scheduled dose, the subject will be instructed to skip the missed dose and resume at the next regularly scheduled time; thus, subjects will be instructed not to double a dose to make up for a missed dose if within 48 hours of the next dose. Investigators may choose to have subjects take the weekly dose divided over the day (i.e. BID, TID).

During the Pegloticase + MTX Period, MTX should be taken 1 to 3 days prior to the pegloticase infusion and one additional weekly dose after the last infusion (at Week 22) for subjects who have not stopped pegloticase due to study sUA Discontinuation Criteria. If a subject is not able to take the MTX 1 to 3 days prior to the pegloticase infusion, MTX must be taken  $\geq$ 60 minutes prior to the pegloticase infusion.

During the Pegloticase + MTX Period, if a subject becomes unable to tolerate the MTX the dosage may be decreased.

Subjects will also take folic acid 1 mg orally every day beginning at Week -4 (the start of MTX) until prior to the Week 24 Visit.

**Pegloticase:**

All subjects who meet the inclusion/exclusion criteria and tolerate oral MTX 15 mg weekly during the MTX Run-in Period will receive pegloticase at a dose of 8 mg administered IV every 2 weeks for a total of 12 infusions from Day 1 through Week 22 inclusive (Pegloticase + MTX Period). The date and start and stop time of infusion will be recorded. Subjects will not be fasting on the day of infusion and will be encouraged to have a snack or normal meal before or after the infusion.

All subjects will receive standardized prophylactic treatment to reduce the risk of acute gout flares, beginning  $\geq$ 1 week before the first dose of pegloticase and continuing throughout the pegloticase treatment per American College of Rheumatology guidelines [[Khanna D et al. 2012](#)].

Standardized IR prophylaxis consisting of pre-treatment with an antihistamine, acetaminophen and a corticosteroid will accompany each infusion.

**Dosage Form and Strength Formulation (Pegloticase and MTX):**

Pegloticase will be supplied as KRYSTEXXA which is commercially available in the United States and will be packaged in sterile, single-use 2-mL glass vials with coated (latex-free)

rubber injection stopper to deliver pegloticase as 8 mg of uricase protein in 1 mL volume. Pegloticase will be administered as an admixture of 8 mg in 50 mL of 0.45% or 0.9% Sodium Chloride Injection, United States Pharmacopeia (USP) for IV infusion by gravity feed or infusion pump.

An alternative presentation of pegloticase is filled into sterile, single-use 50-mL glass vials with a Fluorotec-coated rubber injection stopper which delivers 8 mg uricase in a 50 mL ready-to-use solution.

Pegloticase will not be administered as an IV push or bolus.

MTX 2.5 mg tablets for oral administration will be provided to all subjects as a commercially available generic.

#### **Duration of Treatment and Follow-up:**

**Screening:** Up to 35 days prior to the Pegloticase + MTX Period.

**MTX Run-in Period (Week – 4 to Day 1):** 4 weeks of MTX dosing prior to initial pegloticase dose.

**Pegloticase + MTX Period (Day 1 through Week 24):** 24 weeks (infusion visits every 2 weeks) plus the End-of study/Early Termination Visit (Week 24)

**Week 24/End-of-study/Early Termination Visit:** Week 24 or earlier if the subject withdraws consent to participate in the study.

**End of Pegloticase Infusions Visit (if applicable):** If the subject discontinues pegloticase treatment prior to infusion Week 22, such as due to the sUA Discontinuation Criteria, the subject will complete this visit within approximately 2 weeks of the last infusion. Subjects will continue in study for Follow-Up visits, including the 30-day Follow-Up Email/Phone call, Week 24/End of Study/Early Termination and 3 Month Post-Treatment Follow-up Visits.

**Safety Follow-up Visit:** All subjects will receive a safety Follow-up phone call/e-mail/visit approximately 30 days after the last dose of pegloticase to assess if any AE/SAE's have occurred and to confirm if any previous AE/SAEs have resolved. Subjects who receive at least one dose of MTX and are females of childbearing potential, will receive a safety Follow-up phone call/e-mail/ approximately 30 days after the last dose of MTX to verify at least one ovulatory cycle has occurred after the last dose of MTX. If the subject has not ovulated, a urine pregnancy test will be performed. Subjects who receive at least one dose of MTX and are non-vasectomized males, a phone/e-mail/site visit inquiry will be conducted 3 months after MTX discontinuation regarding partner pregnancy (inquiry can occur during the 3-month Post-Treatment Follow-up). If the subject discontinues treatment but continues in the study, then this Follow-up visit may be replaced by a scheduled study visit.

**3-Month Post-Treatment Follow-up Visit:** All subjects will be followed for a minimum of 3 months following the last infusion, with follow-up after Week 24 as warranted.

#### **Restricted Medications**

Subjects will be directed to discontinue current urate-lowering therapy prior to screening. Other medications used at the time of study initiation may be continued at the discretion of the Investigator.

The following medications are prohibited during the study:

- Concomitant therapy with allopurinol, febuxostat or other urate lowering medications or a polyethylene glycol-conjugated drug
- Systemic or radiologic treatment for ongoing cancer, excluding non-melanoma skin cancer
- Current or chronic treatment with systemic Immunosuppressive agents

### **Removal of Subjects from Treatment or Assessment**

Every effort should be made to retain a subject in the study to monitor their safety. However, subjects may withdraw consent or discontinue treatment or participation from the study at any time, without prejudice to further treatment. In addition, the Investigator may terminate a subject's treatment at any time. The primary reason for discontinuation from the study and/or study drug should be recorded on the eCRF.

### **Criteria for Evaluation:**

Safety and tolerability assessments will include monitoring and recording of all AEs, whether or not drug-related, measurement of vital signs, physical examinations, 12-lead ECG and monitoring of hematology and blood chemistry.

Efficacy will be assessed by sUA levels.

The incidence of anti-uricase and anti-polyethylene glycol antibodies will be assessed at specified time points.

### **Infusion Speed-Limiting Criteria:**

Infusion speed-limiting criteria will be met if a subject experiences any severe (Grade  $\geq 3$ ) IRs or any other severe AEs within 24 hours of receiving pegloticase infusion and attributed to the infusion and not any other underlying disease process. The signs and symptoms of the severe IRs are usually prolonged (e.g., not rapidly responsive to symptomatic medication and/or brief interruption of infusion) or recurrent following initial improvement. Possible associated signs and symptoms of IRs may include but not limited to:

- Respiratory: difficulty breathing with wheezing or stridor; upper airway swelling (lip, tongue, throat, uvula, or larynx); respiratory distress manifested as at least 2 or more of the following: tachypnoea, increased use of accessory respiratory muscles, cyanosis, recession, grunting
- Cardiovascular: hypertension, tachycardia, measured hypotension, a decreased level of consciousness, loss of consciousness
- Dermatological or mucosal: generalized urticaria (hives) or generalized erythema, angioedema, generalized pruritus with skin rash

If  $\leq$  one-eighth of subjects meet infusion speed-limiting criteria at the same infusion duration after 3 subjects and after 6 subjects, then enrollment may continue at the same infusion

duration. If  $\leq$  one-eighth of subjects meet infusion speed-limiting criteria at the same infusion duration after 10 subjects, then enrollment may continue at the next progressively shorter infusion duration.

If  $>$  one-eighth of subjects meet infusion speed-limiting criteria, then enrollment at that infusion duration may be suspended. The Safety Review Committee must confirm that infusion speed-limiting criteria were met, prior to additional patients being enrolled.. In the event that  $>$  one-eighth of subjects meet infusion-speed limiting criteria at the initial 60-minute infusion duration, then the study may be revised or terminated (after internal review and assessment).

If an anaphylaxis event occurs in any subject, further dosing with pegloticase for that subject will be terminated.

If any anaphylaxis event or SAE related to pegloticase infusion occurs with any subject, all pertinent data will be provided for expedited review to the Adjudication Committee (for the purpose of adjudicating AESIs) and the SRT/SRC. If any anaphylaxis event or SAE related to pegloticase infusion occurs with any subject, real-time with expedited review of patient profiles and/or relevant data available in the electronic data capture will occur.

#### **Individual Subject sUA Discontinuation Criteria:**

Subjects with a pre-infusion sUA level  $>6$  mg/dL at 2 consecutive study visits beginning with the Week 2 Visit will discontinue treatment, but continue on study as described in [Section 9.4.3](#).

Note: The sUA Discontinuation Criteria only pertain to individual subjects and are not sUA Discontinuation Criteria for a group or specific infusion duration.

#### **Statistical Analyses:**

##### Primary Endpoint

[figure not shown]
The primary endpoint is the incidence of subjects experiencing IRs (including anaphylaxis) related to pegloticase from Day 1 to Week 24 in the cohort chosen to be the most desirable duration for infusion.

##### Secondary Endpoints

The secondary endpoints will be assessed for the cohort chosen to be the most desirable duration for infusion and include:

- The proportion of Month 6 (Weeks 20, 22 and 24) responders, defined as subjects achieving and maintaining sUA  $<6$  mg/dL for at least 80% of the time during Month 6.
- The proportion of subjects who experienced any of the following events: IR leading to discontinuation of treatment, anaphylaxis, or meeting Individual Subject sUA Discontinuation Criteria.
- Time to any of the following events: IR leading to discontinuation of treatment, anaphylaxis, or meeting Individual Subject sUA Discontinuation Criteria (two consecutive pre-infusion SUAs  $> 6$  mg/dL).

Exploratory Endpoints

Pharmacokinetic and Anti-drug Antibody Endpoints

- PK of pegloticase.
- Incidence and titer of anti-PEG and anti-Uricase IgG antibodies.

Safety Endpoints

- Incidence of IRs, anaphylaxis, gout flares, cardiovascular events and the AE/SAE profile overall and potentially attributed to the combination of pegloticase and MTX.
- The proportion of subjects who experienced IR leading to slowing down of the infusion rate or discontinuation of treatment.
- The time to first IR leading to slowing down of the infusion rate or discontinuation of treatment.
- Time to first IR.
- The proportion of subjects who were able to complete all infusions over the assigned treatment duration length or a lesser time, without clinically requiring an increased infusion time
- The proportion of infusions completed over the assigned duration length or a lesser time, without clinically requiring an increased infusion time.
- Laboratory tests
- Vital signs & physical examinations

Statistical Analysis on Primary and Secondary Endpoints

The primary analysis will be performed using the modified intention-to-treat (mITT) population, defined as all enrolled subjects who received  $\geq 1$  dose of pegloticase. The primary endpoint is the incidence of subjects experiencing an IR (including anaphylaxis) related to pegloticase from Day 1 to Week 24 in the cohort chosen to be the most desirable duration for infusion (e.g. this may be the 30-minute infusion cohort if infusion-speed limiting criteria not met). This endpoint will be analyzed with a summary of the incidence and the corresponding two-sided 95% confidence interval. Additionally, this endpoint will be analyzed for each of the other infusion duration cohorts.

The proportion of responders during Month 6 will be summarized, along with a two-sided 95% exact (Clopper-Pearson) confidence interval for the proportion. A responder is defined as a subject for whom the proportion of time that the sUA-time curve is  $< 6$  mg/dL during Month 6 (Weeks 20, 22 and 24) is at least 80%. The proportion of time that the sUA level is below 6 mg/dL is defined as the ratio of the time during which the sUA level remains below 6 mg/dL (using linear interpolation, if necessary) to the entire time interval during Month 6. The proportion of subjects experiencing any of the following events: IR leading to discontinuation of treatment, anaphylaxis, or meeting Individual Subject sUA Discontinuation Criteria will be presented. This composite endpoint, each individual component of the composite and the proportion of subjects who experienced an IR leading to the slowing down of the infusion rate or discontinuation of treatment will be analyzed for each infusion duration regimen with a summary of the incidence and the corresponding two-sided 95% confidence interval.

Time to subjects meeting any of the composite endpoint criteria will be assessed by assigned treatment regimen. Kaplan-Meier (KM) estimates of the time to event will be presented, along with the corresponding quartiles and two-sided 95% CI for the median time if there are sufficient number of events to perform the analysis. The individual components of the composite endpoint, the time to first IR leading to slowing down of the infusion rate, time to first IR and time to first instance of IR leading to slowing down of the infusion rate or discontinuation of treatment will be summarized in the same way as the composite.

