**Week 24/End of Study/Early Termination Visit.**

Subjects must be able to tolerate MTX at a dose of 15 mg during the 4-week MTX Run-in Period (prior to Day 1) to be eligible to participate in the Pegloticase + MTX Period.

Subjects who are unable to tolerate MTX at a dose of 15 mg during the MTX Run-in Period will be considered screen failures.

Female subjects who take at least one dose of MTX and who are females of childbearing potential, will receive a safety Follow-up phone call/e-mail approximately 30 days after the last dose of MTX to verify at least one ovulatory cycle has occurred after the last dose of MTX. If the subject has not ovulated, a urine pregnancy test will be performed. For those subjects who take at least one dose of MTX and who are non-vasectomized males an inquiry will be conducted at the Post-Treatment 3-month Follow-up visit (or 3 months after the subject's last dose of MTX) after MTX discontinuation regarding partner pregnancy.

All subjects who complete the Run-In Period and meet the inclusion/exclusion criteria will receive the first pegloticase infusion on Day 1. All subsequent doses and study visits will be scheduled based on the Day 1 visit date.

Prior to the Treatment Period, subjects will begin taking at least one of the per protocol standard gout flare prophylaxis regimen (colchicine 0.6 mg/day and/or nonsteroidal anti-inflammatory drug (NSAID) and/or low dose prednisone <10 mg/day) for  $\geq 1$  week before the first dose of pegloticase and continues flare prophylaxis throughout the pegloticase treatment period per American College of Rheumatology guidelines [Khanna D et al. 2012].

For IR prophylaxis, fexofenadine (180 mg orally) will be taken the night before each infusion; fexofenadine (180 mg orally) and acetaminophen (1000 mg orally) will be taken the morning of each infusion; and methylprednisolone (125 mg IV) over an infusion duration between 10 and 30 minutes, will be administered immediately prior to each infusion.

During the Pegloticase + MTX Period, all subjects will receive pegloticase 8 mg every 2 weeks administered IV for a total of 12 infusions from Day 1 through Week 22, inclusive.

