### 3.4 Endpoint Analysis

Potential intercurrent events (ICE) like discontinuing from the treatment may occur during the study. Subjects who discontinue from the treatment will be encouraged to stay in the study after and data will be collected through planned study completion. These intercurrent events will be addressed using different strategies in the efficacy and safety analyses as appropriate.

In general, treatment policy strategy will be used to account for the ICEs for defining estimands corresponding to continuous efficacy endpoints. For binary responder endpoints, composite strategy will be used. Safety endpoints will be assessed using a while-on-treatment strategy.

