### 3.6.3.5 Additional Safety Endpoints

The following safety endpoints will be summarized descriptively for the safety analysis set by assigned infusion duration:

- The proportion of subjects who experienced IR leading to slowing down of the infusion rate or discontinuation of treatment (composite endpoint and for each individual component; separate analyses for reported events and adjudicated events) (safety analysis set).
- The proportion of subjects who completed all infusions over the assigned treatment duration length or a lesser time, without clinically requiring an increased infusion time (safety analysis set) will be summarized. Subjects who discontinue treatment prematurely will not be considered to have completed all infusions.
- The proportion of infusions completed over the assigned duration length or a lesser time, without clinically requiring an increased infusion time will be summarized for the safety analysis set on the infusion level and on the subject-specific level using two different denominators each:
  - Infusion level (will be reported as a proportion and a percentage):
    - The number of infusions completed over the assigned treatment duration length or a lesser time, without clinically requiring an increased infusion time / total number of infusions planned for all subjects (12 x number of subjects in the assigned treatment duration group).
    - The number of infusions completed over the assigned treatment duration length or a lesser time, without clinically requiring an increased infusion time / total number of infusions completed prior to discontinuation of treatment planned for all subjects.
  - Within-subject level (reported descriptively as a continuous variable with 95% sign test-based confidence intervals provided around the median):
    - For each subject, the subject-specific number of infusions completed over the assigned treatment duration length or a lesser time, without clinically requiring an increased infusion time / subject's total number of infusions planned (12 total).
    - For each subject, the subject-specific number of infusions completed over the assigned treatment duration length or a lesser time, without clinically requiring an increased infusion time / subject's total number of completed infusions prior to discontinuation of treatment.

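### The subject-level endpoint on completing all infusions scores every early stop as a failure, so it mixes infusion tolerance with urate non-response and dropout and has no on-treatment counterpart

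*Protocol*

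**What the plan says.** The protocol (synopsis, Safety Endpoints; 9.7.1.5) defines a subject-level safety endpoint: the proportion "who were able to complete all infusions over the assigned treatment duration length or a lesser time", with the condition that no longer infusion was clinically required. Protocol 9.7.7 gives it a two-sided 95% Clopper-Pearson interval. The protocol does not say how a subject who stops pegloticase early is counted.

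SAP 3.6.3.5 settles that: "Subjects who discontinue treatment prematurely will not be considered to have completed all infusions". It makes no exception by reason for stopping, and the denominator is the safety analysis set by assigned duration.

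Three other provisions bear on this:

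- Subjects are to receive pegloticase "for a total of 12 infusions from Day 1 through Week 22, inclusive" (protocol synopsis, Study Design).
- Subjects with pre-infusion sUA above 6 "mg/dL at 2 consecutive study visits beginning with the Week 2 Visit will discontinue treatment, but continue on study" (synopsis, Individual Subject sUA Discontinuation Criteria). The note beneath reads: "The sUA Discontinuation Criteria only pertain to individual subjects and are not sUA Discontinuation Criteria for a group or specific infusion duration".
- SAP 3.4 states: "Safety endpoints will be assessed using a while-on-treatment strategy".

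For the related shares of infusions, SAP 3.6.3.5 plans two denominators, at both infusion and within-subject level. One is the planned number; the other is the number received before stopping (at infusion level, "total number of infusions completed prior to discontinuation of treatment planned for all subjects"). The proportion of subjects has one version only.

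**The concern.** The endpoint's qualifying condition concerns a clinical need for a longer infusion, so it will be read as a measure of whether the 30-, 45- or 60-minute infusion was tolerated. Under the SAP rule a subject can fail in two quite different ways. An infusion may have had to be lengthened or abandoned, or treatment may have ended for another reason: the mandatory sUA stop, loss to follow-up, withdrawal of consent, pregnancy or termination by the sponsor (the list in protocol 9.4.3.1). The single proportion does not separate them.

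Counting an early stop as a failure is a composite strategy. SAP 3.4 states a while-on-treatment strategy for safety endpoints and does not list this one as an exception. What is at stake is interpretation. Two cohorts with the same tolerance of the infusion could show different proportions because urate response or dropout differed, and two cohorts with different tolerance could show the same one.

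**Working it through.** **The plan's own design figure.** No expected value is given for this endpoint. The only sizing statement (protocol 9.7.9; SAP 1.1.3) concerns infusion reactions: N = 110, a 5% rate, and more than 80% probability that the upper exact 95% bound is below 13%. The upper Clopper-Pearson bound is 12.67% for 7/110 and 13.83% for 8/110, so at most 7 events are allowed. P(X ≤ 7 | n = 110, p = 0.05) = 81.4%. The stated figure reproduces, and the issue here does not touch it.

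**How one subject is scored.** Suppose sUA exceeds 6 mg/dL at Weeks 2 and 4 and the Week 4 result is known before that infusion. The subject has received the Day 1 and Week 2 infusions, 2 of 12. If both ran at the assigned duration, the subject scores:

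- 2/2 on the within-subject share with the completed-infusion denominator;
- 2/12 on the share with the planned denominator;
- failure on the subject-level endpoint.

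**Effect with no intolerance at all.** Let s be the proportion stopped for reasons other than infusion tolerance. The documents give no such rate for pegloticase with MTX. The one urate response figure they give, 42% (protocol 7.1.2 and 7.2), is for pegloticase without MTX and is not a stop rate. The values of s below are assumptions. With N = 110 and no infusion ever needing more time, the endpoint reads 1 − s:

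| s (assumed) | Count | Endpoint | Exact 95% CI |
|---|---|---|---|
| 20% | 88/110 | 80.0% | 71.3% to 87.0% |
| 30% | 77/110 | 70.0% | 60.5% to 78.4% |
| 40% | 66/110 | 60.0% | 50.2% to 69.2% |

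A cohort with no early stops in which 22 of 110 subjects needed slower infusions would also read 88/110 = 80.0%.

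**Composition of the failures.** Let i be the proportion with infusion intolerance, s the sUA-rule stops and d other dropout, treated as independent for simplicity. Then:

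- completion = (1 − s)(1 − d)(1 − i);
- failures without intolerance = (1 − i)[1 − (1 − s)(1 − d)].

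Take i = 5%, the planned rate for any infusion reaction. It stands in for reactions that force slowing or stopping, and is probably high for that purpose.

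| s | d | Completion | Failures without intolerance / all failures |
|---|---|---|---|
| 5% | 0 | 90.25% | 4.75% / 9.75% = 49% |
| 10% | 0 | 85.5% | 9.5% / 14.5% = 66% |
| 20% | 0 | 76.0% | 19.0% / 24.0% = 79% |
| 40% | 10% | 51.3% | 43.7% / 48.7% = 90% |

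Counting intolerance alone would give 95% in every row. On these assumptions the two kinds of failure are about equal when other stops are near 5%.

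**What the planned tables recover.** If 20% stop after two infusions and nothing is ever slowed, the infusion-level share is 0.80 + 0.20 × 2/12 = 83.3% on the planned denominator and 100% on the completed one. The mixing is therefore visible at infusion level. At within-subject level the share is summarised as a continuous variable with an interval around the median, which does not show how many subjects are at 100%.

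**The case against.** The strongest reply is that the SAP follows the endpoint's own words: twelve infusions are planned, and someone stopped after two has not completed them all. That stands. The rule is openly stated, and counting only infusions received defines a different endpoint.

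Second, much of the needed information is already planned:

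- subject-level infusion reactions leading to slowing or discontinuation, as a composite and by component, reported and adjudicated (SAP 3.6.3.5);
- sUA-rule stops (SAP 3.4.2.1 and 3.4.2.2);
- treatment discontinuations with reasons by cohort, and shifts from the assigned duration (SAP 3.3.1);
- changes in planned duration and interrupted infusions (SAP 3.6.2).

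This largely stands and lowers the stakes. None of these tables, however, gives the proportion of subjects whose every received infusion stayed within the assigned duration. The infusion-reaction endpoint omits lengthening for other reasons, which investigators may choose at their discretion, and the exposure rows do not say whether a change was clinically required.

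Third, a reader might take the note that "The sUA Discontinuation Criteria only pertain to individual subjects and are not sUA Discontinuation Criteria for a group or specific infusion duration" to mean that sUA stops carry no information about tolerance. The documents do not support that. The note says to whom the rule applies. Protocol 7.1.2 reports that sUA above 6 mg/dL preceded the first infusion reaction in 20 of 22 subjects, and 7.1.3 says the risk is higher above that level. It follows that a version counting only received infusions would score some higher-risk early stoppers as successes, so replacing the present definition would exchange one distortion for another.

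Fourth, SAP 3.4 speaks of strategies applied as appropriate, and a specific rule can override a general one. That is fair. The departure needs a stated exception and does not amount to a contradiction in the analysis.

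**Conclusion.** The subject-level completion proportion mixes infusion tolerance with urate non-response and dropout. It departs from the strategy stated in SAP 3.4 without saying so, and it lacks the on-treatment version that its sibling measures have. These facts rest on the SAP text and need no assumption.

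The size does need one. At 20% stops for other reasons and no intolerance, 110 subjects would show 80.0% (71.3% to 87.0%); at 40%, 60.0% (50.2% to 69.2%). A reader might infer that most failures will be unrelated to the infusion, or that the proportion says nothing about tolerance. The documents do not establish either: they give no stop rate with MTX, the independence used above is a simplification, and loss of urate response is linked to infusion reaction risk.

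Nor does the point reach the primary endpoint, the sample size or the choice of cohort, which rests on the speed-limiting criteria. The endpoint is descriptive and no statistical testing is planned. This is a modest gap in reporting that is worth closing because closing it is cheap.

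**What to change.** In SAP 3.6.3.5, keep the proportion completing all 12 infusions as defined, and make two additions:

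1. Beside it, report the proportion of subjects in whom every infusion received was completed within the assigned duration without clinically requiring more time, with its exact 95% CI. A stop for an infusion reaction or another infusion-related event counts as a failure; a stop under the sUA rule or for another reason does not.
2. Split the failures on the all-12 version into infusion lengthened, stop for an infusion reaction or infusion-related event, sUA rule, and other.

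In SAP 3.4, state that the all-12 version is a composite-strategy exception to the while-on-treatment approach.

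The cost is a few sentences and a few table rows from data already collected; no clinical rule changes. The drawback is that early stoppers have fewer infusions in which to fail, so the added row is optimistic. A footnote should say that it is to be read with the all-12 row.
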